# **Risk Assessment**

Important/potential/risk of clinical significance	Summary of data/rationale for risk	Mitigation strategy
	therapy, to avoid the risk of hematoma following the injection.	Participants with any medical condition that in judgment of the investigator would make intramuscular injection unsafe will be excluded from study enrollment.
mRNA-CR-04 vaccine		
Myocarditis/pericarditis	Myocarditis/pericarditis are considered as an important identified risk for marketed mRNA COVID-19 vaccines [EMA, 2021a; EMA, 2021b; FDA, 2021a; FDA, 2021b] The estimated reporting rates of myocarditis in younger adults [25- to 29-year old] following the first and the second doses of BNT162b2 vaccine were 0.7 and 5.7 per 100 000, respectively and following the first and the second doses of mRNA-1273 vaccine were 1.8 and 11.2 per 100 000, respectively [CDC, 2021]. The same reporting trend was observed following booster mRNA vaccination, except for age, with most cases reported in older adults [ACIP, 2021].	Participants at increased risk of myocarditis/pericarditis or with medical history of myocarditis/pericarditis are excluded from study enrollment. Participants will also be instructed (via informed consent form) to be alert for symptoms of myocarditis/pericarditis and immediately contact the site if any of these symptoms occur. Participants will be tested for cardiac troponin I and undergo EKG at the screening and on D8 after study intervention administration. Participants will receive close medical supervision and medical assessments (e.g., laboratory testing) during the study. Moreover, myocarditis/pericarditis will be collected as an AESI and adjudicated (refer to Section 8.3.8,Section 8.4.4 and Section 10.3.5)

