# 8.3.8. Cardiac adjudication

Myocarditis and pericarditis are considered as important potential risk and are collected as AESI. All surveillance EKGs occurring at Screening, Day 8, and unscheduled visits, will be reviewed by an independent external cardiologist in a blinded fashion to identify potential myocarditis or pericarditis cases. All EKGs identified with changes suggestive of potential myocarditis and pericarditis and related available medical records requested from treating cardiologists evaluating potential cases of myocarditis and pericarditis, will then be provided to an independent external adjudication committee for case adjudication according to the case definition from the Brighton Collaboration [Sexson, 2022]. The committee members will remain blinded to study intervention assignment. For details on who will perform the reading and adjudication activities, please refer to the separate list of vendors.

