#### 8.4.4.2.1. Myocarditis and pericarditis: definitions and assessment

All potential cases of myocarditis and pericarditis will be provided to the independent external adjudication committee for case adjudication according to the case definition from the Brighton Collaboration [Sexson, 2022].

Source documentation of suspected cases of myocarditis and pericarditis to be provided for adjudication as it becomes available may include (but are not limited to) the following:

- Clinical notes (including history, physical examination, EKG findings)
- Emergency department notes (including history, physical examination, EKG findings)
- Hospital discharge summary
- Clinical laboratory values
- Concomitant medications

- Chest X-ray reports
- Cardiac imaging

Following adjudication, all probable and definitive cases of myocarditis and pericarditis will be reviewed by SRT (blinded data review until Part A Day 15 interim analysis, unblinded data review subsequently) and iSRC (unblinded data review). An ad-hoc iSRC will be conducted on receiving any probable or definitive cases of myocarditis and pericarditis. An independent external cardiologist may be part of iSRC to provide input on the potential myocarditis and pericarditis cases.

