## 10.1.5. Committees structure

The study will be overseen by an SRT, and iSRC operating under a charter.

The SRT is an internal team, with representatives of different functions (including safety physician, a CSL and a biostatistician) involved in the conduct of the study/project.

A SRT is in place for each GSK product. It comprises of a global cross-functional team responsible for the ongoing assessment of benefit-risk for a product. The SRT contribute to the continual assessment of incoming new efficacy and safety information.

The iSRC is an internal committee including a GSK safety physician, a CSL and a biostatistician who are not otherwise involved in the conduct of the project.

More details on the composition, objectives, and responsibilities of the iSRC will be described in the charter.

Furthermore, to enhance independent, systematic, and standardized identification, processing and review of probable or confirmed cases of myocarditis or pericarditis; an independent external cardiologist will review and assess all performed EKGs (Screening, Day 8, unscheduled visits) and an independent adjudication committee will perform case adjudication according to the case definition from the Brighton Collaboration [Sexson, 2022]. Details of data collection and frequency of data review are provided in Section 8.4.4.2.1.

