#### 6.2.3.11. AESIs

GSK MedDRA queries will be used to identify AESI:

- PIMD: refer to Table 12 from the protocol
- Severe hypersensitivity (including anaphylaxis): Grade 3 unsolicited AEs under MedDRA SMQ hypersensitivity, narrow search (includes anaphylaxis), with an onset within 24 hours after dosing
- Myocarditis/Pericarditis. In addition to identification based on the medical and scientific judgement of the investigator, the following list of MedDRA SMQs will be used: Cardiac arrhythmia, Cardiac failure, Cardiomyopathy, Ischaemic heart disease, Non-infectious myocarditis/ pericarditis, narrow search.
- Virologically confirmed COVID-19 cases: In addition to identification based on the medical and scientific judgement of the investigator, AEs under MedDRA SMQ COVID-19, narrow search will be used

This PIMD, Virologically confirmed COVID- 19 cases, Myocarditis and Pericarditis queries may be revised based on MedDRA dictionary.

AESI summaries will include AE identified by either the investigator or the MedDRA queries.

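### The SAP does not use the external committee's verdict on myocarditis/pericarditis: a confirmed case with no site AE can be missing from the AESI tables, and a rejected event is shown without its status

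*SAP*

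**What the plan says.** **Protocol.** Section 8.3.8 has the surveillance EKGs (Screening, Day 8, unscheduled visits) go to an outside reader: they "will be reviewed by an independent external cardiologist in a blinded fashion to identify potential myocarditis or pericarditis cases". EKGs with suggestive changes, and the related medical records, "will then be provided to an independent external adjudication committee for case adjudication according to the case definition from the Brighton Collaboration". On blinding it adds: "The committee members will remain blinded to study intervention assignment". Section 8.4.4.2.1 widens the intake beyond EKG findings: "All potential cases of myocarditis and pericarditis will be provided to the independent external adjudication committee for case adjudication". Section 10.1.5 states the purpose, which is "to enhance independent, systematic, and standardized identification" of cases, and the risk table in section 2.3 says that "myocarditis/pericarditis will be collected as an AESI and adjudicated". The one stated use of the verdict is in section 8.4.4.2.1: probable and definitive cases go to the SRT and the iSRC, with an ad-hoc iSRC meeting.

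**SAP.** Section 6.2.3.11 identifies this AESI by investigator judgement plus queries: "the following list of MedDRA SMQs will be used: Cardiac arrhythmia, Cardiac failure, Cardiomyopathy, Ischaemic heart disease, Non-infectious myocarditis/ pericarditis, narrow search". It closes with the counting rule: "AESI summaries will include AE identified by either the investigator or the MedDRA queries". Section 4.2.1.3 summarizes each AESI by relationship, severity, outcome and action taken. Sections 4.2.1.1 and 4.3.1.1 tabulate AESIs up to D31 (part of the primary endpoint) and up to M6 (the secondary safety endpoint), with exact 95% CIs and detailed AESI listings. None of these sections, nor the changes-to-protocol section 4.9, mentions adjudication, the external cardiologist or the case definition.

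**The concern.** The trial pays for an independent, standardized classification of the main cardiac risk named for the platform, and the analysis plan then leaves it out. Two things can follow.

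- **A confirmed case can be absent.** The central read can raise a case that the site did not. If the committee calls it probable or definitive but the site has entered no AE, there is no record for the investigator route or the queries to find. The SAP plans no EKG tabulation in which it would appear instead. The same case would have prompted an ad-hoc iSRC meeting.
- **A rejected event stays in unmarked.** An arrhythmia or ischaemic event that matches a query is summarized under myocarditis/pericarditis whatever the committee decides, and the reader is not told the decision.

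At stake is how this AESI reads in the primary and secondary safety tables, where groups are small enough for one event to be visible.

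**Working it through.** **Tracing a case through the text**

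| Step | Source | Does the verdict enter? |
|---|---|---|
| Blinded EKG read and committee classification | Protocol 8.3.8, 8.4.4.2.1 | It is produced here |
| Use of the verdict | Protocol 8.4.4.2.1 | SRT and iSRC review only |
| When an abnormal EKG is an AE | Protocol 10.3.1 | No; clinical significance is the investigator's judgement |
| When an AE becomes an AESI | Protocol 8.4.4.2 | No; enough evidence for the diagnosis, committee not named |
| Protocol tabulation of AESIs | Protocol 9.4.1, 9.4.2.1 | No |
| SAP identification and counting | SAP 6.2.3.11 | No; two sources only |
| SAP summaries | SAP 4.2.1.3 | No adjudication status |

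No step requires the verdict to be sent back to the site or the AE record to be updated after it. A confirmed case reaches the tables only through a site AE record, and a rejected one is neither removed nor marked.

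**Query content.** Of the five SMQs, one (non-infectious myocarditis/pericarditis) names the condition. The other four are arrhythmia, cardiac failure, cardiomyopathy and ischaemic heart disease. Protocol 8.4.4.2 keeps events that only might lead to the diagnosis as AEs, not AESIs, until it is made; the SAP query counts them if they match.

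**Size of one case.** The plan gives no figure on this point. The group size, 18 vaccinees per dose, is from SAP section 5, whose probabilities reproduce: 1 − 0.95^18 = 0.603 and 1 − 0.90^18 = 0.850.

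Exact (Clopper-Pearson) limits, the SAP's own method:

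- 0/n: upper limit = 1 − 0.025^(1/n). For n = 18 this is 18.5%; for n = 36, 9.7%.
- 1/n: lower limit = 1 − 0.975^(1/n), upper limit = 97.5% point of Beta(2, n − 1). For n = 18: 1/18 = 5.6% (0.1 to 27.3%). For n = 36, the pooled 10 µg group (18 + 18): 1/36 = 2.8% (0.1 to 14.5%).

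One case added or marked moves a dose line by 5.6 percentage points, or the pooled 10 µg line by 2.8.

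**How often it could arise.** Planned vaccinees: 3 × 18 + 2 × 18 = 90. The highest myocarditis rate in the protocol's risk table is 11.2 per 100 000 (second dose of a marketed mRNA vaccine, ages 25 to 29). If it applied here, the expected number is 90 × 11.2/100 000 = 0.010. That is a rate of reported cases, so it need not describe EKG surveillance, and the four broader queries will match commoner events. The documents give no rate for either. For assumed rates of 0.5%, 1% and 2%, the chance of at least one event among 90, 1 − (1 − p)^90, is 36%, 60% and 84%.

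**The case against.** The strongest reply is that the SAP does what the protocol's analysis sections ask. Protocol 9.4.1 and 9.4.2.1 tabulate AESIs with no reference to adjudication, and nowhere does the protocol say that the verdict defines the count. On this view the committee serves safety oversight. That stands. A reader might infer that the SAP contradicts the protocol; the documents do not support it, because there is no stated analysis rule to break.

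Second, a confirmed case that is never counted needs several things to fail. Clinically significant EKG abnormalities are AEs (Protocol 10.3.1), an AE must be reported as an AESI once the evidence suffices (8.4.4.2), the investigator reviews suggestive Day 8 findings (8.4.4.2.1), and any AE matching a query is counted even if the investigator did not call it an AESI. This also stands, and it makes the gap narrow. It does not close it, because the verdict need not return to the site.

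Third, keeping rejected events is the cautious choice in a first-in-human trial, and it fits the safety estimands, which use all data whatever intercurrent event occurs. This is a good reason against replacing the inclusive count. It is no reason to withhold the verdict from the reader.

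A reader might also infer that, with the sponsor unblinded in Part B, the committee is the only blinded assessment left. It is not: site personnel who evaluate participants stay blinded (Protocol 6.3.4), investigators do so until end of study (9.5.1), and the cardiologist reads EKGs blinded (8.3.8). What the committee adds is independence and a standard case definition.

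**Conclusion.** The point holds as an omission in the SAP. The committee's verdict is obtained for all potential cases and is used nowhere in the planned analysis, so the AESI tables can omit a case it confirmed and will show one it rejected with nothing to mark it. The size is one case: 0% to 5.6% in a dose group, with the exact upper limit going from 18.5% to 27.3%. It would be tempting to say that one case decides the result. It does not: there is no hypothesis test, the two intervals overlap heavily, and counted AESIs are also listed individually.

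The missed-case half assumes that the site enters no AE for an adjudicated case, which the documents allow but which should be rare. The rejected-event half needs only a cardiac AE that matches one of the four broader queries. An investigator could revise a report after the verdict, which would narrow the gap, but neither document requires it. The change is worth making because the data will already exist and the cost is small.

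**What to change.** - **SAP 6.2.3.11:** for myocarditis/pericarditis, add a third identification source: *or adjudicated as probable or definitive by the external committee*. Let it draw on the committee's records, so that it does not depend on a site AE.
- **SAP 4.2.1.3:** keep the inclusive count. Beside it, tabulate by group the number adjudicated as probable or definitive.
- **AESI listing:** add the verdict (probable/definitive, rejected, not adjudicated) for each myocarditis/pericarditis event.

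Do not replace the inclusive count with the adjudicated one. That would lower the reported safety count and depart from the AESI tabulation in Protocol 9.4.1.

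Cost: SAP wording, one listing column, and transfer of the verdicts, with event dates so that cases fall in the D31 or M6 table, into the analysis dataset. There are no new assessments and no added burden on participants.

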## 6.2.4. Display of decimals

#### 6.2.4.1. Percentages

Percentages will be displayed with one decimal except for 100% in which case no decimal will be displayed.

## 6.2.4.2. Differences in percentages

Differences in percentages and their corresponding confidence limits will be displayed with one more decimal than the maximum number used to display the individual percentages, for example the difference between two percentages displayed with one decimal will be displayed with two decimals.

## 6.2.4.3. Demographic/baseline characteristics statistics

The mean, median, and SD for continuous baseline characteristics (height, weight, BMI, pre-dose body temperature) will be presented with one decimal.

The minimum and maximum values and quartile values (if required) will be presented with the same number of decimals as the observed values.

The minimum and maximum of transformed height variables will be displayed with no decimals.

The minimum and maximum of transformed weight variables will be displayed with no decimals with the exception of values are below 10kg where one decimal will be displayed.

The maximum and minima of transformed body temperatures will be displayed with one decimal.

## 6.2.4.4. Serological summary statistics

The number of decimals used when displaying GMTs or GMCs and their confidence limits is shown in the following table:

GMT or GMC value	Number of decimals to display
< 0.1	3
>=0.1 and <10	2
>=10 and <1000	1
>=1000	0

When multiple categories of GMT or GMC values are present in the same table, the number of decimals displayed should match that of the smallest category (i.e. the one with the higher number of decimals). For example, if GMT or GMC values of <0.1 appear in the same table as values of >=0.1 and <10, 3 decimals should be displayed for both.

GMT or GMC ratios and their confidence limits will be displayed with 2 decimals regardless of the actual values.

## 6.2.5. Statistical methodology

## 6.2.5.1. Exact confidence intervals around proportions

The exact CIs around within-group proportions are derived using the method of Clopper and Pearson [Clopper, 1934].

